7.0 EVALUATIONS/MATERIAL AND DATA TO BE ACCESSIONED

Timing of protocol therapy administration, response assessment studies, and surgical interventions are based on schedules derived from the experimental design or on established standards of care. Minor unavoidable departures (up to 96 hours) from protocol directed therapy and/or disease evaluations (and up to 1 week for surgery) for valid clinical, patient and family logistical, or facility, procedure and/or anesthesia scheduling issues are acceptable.

7.1 Required Clinical, laboratory and Disease Evaluations

All baseline studies must be performed within **14 days** prior to enrollment and MRI of brain and/or spine within **30 days** prior to enrollment. **Obtain other studies prior to start of subsequent cycles and as otherwise indicated.**

STUDIES TO BE OBTAINED	Pre-study ¹ (Baseline)	Prior to Each Cycle	Q2 weeks Cycle 1	Prior to cycle 4,7,10,13 16,19,22,25	Every six months	When patient is removed from protocol Therapy**
History	X	X	X			X
Physical Exam with neurological exam (Wt, Ht and VS)	X	X	X			X
Performance Status	X	X				X
CBC, platelets and differential	X	X	X ⁵			X
CMP, magnesium phosphorous, calcium, Uric acid	X	X	X ⁵			X
PT, PTT	X					
AM cortisol, Free T4, TSH, (growth hormone if clinically indicated)	X				X	X
Urinalysis / urine dipstick	X			X		X
Urine or serum pregnancy test	X ²					
MRI of brain w/wo contrast	X ³			X		X
MRI spine	X ⁴			X ⁶		X
LP for CSF cytology	X ⁹			X ¹⁰		
Ophthalmology Evaluation ⁷	X				X	X
QOL questionnaire ⁸	X			X		X
Pegylated interferon Diary		X	X			X
Assessment of clinical toxicity/adverse events						X

1-Must be performed within 14 days prior to receiving the study drug with the exception of MRI of brain and spine. MRI of the brain and or spine can be done in within **30 days** prior to enrollment.

2-Required for all females of childbearing potential as a baseline study, then continue to follow institutional guidelines regarding pregnancy testing.

3- With and without contrast; within **30 days** prior to enrollment.

4-For patients with a known history of spinal disease, within **30 days** prior to enrollment on the study or when it is clinically indicated by the treating physician.

5-If no > Grade I toxicity during the previous cycle, then every month in subsequent cycles through cycle 27.

6-For patients with history of spinal disease; obtained at the same time points as MRI brain until no evidence of disease on 2 consecutive spine MRIs. Also when patient is removed from protocol therapy.

7-Ophthalmology evaluation only needed for patients with optic pathway gliomas. (Sooner than interval designated if indicated by neuro-ophthalmologist/ophthalmologist)

8- Children younger than 7 years and older will complete the parent survey only. For any child older than 7 years will complete also the patient questionnaire for Quality of life. QOL questionnaires are only available for English speaking patients. They have not been validated in other languages.

9- LP only if there is evidence of tumor dissemination on spine MRI.

10-Repeat only if cytology showed tumor cells at study entry, until you have 2 consecutive negative cytologies.

** To be completed when patient comes off therapy unless it has been completed within the last 14 days and no toxicity greater than grade 1 was found.

This table only includes evaluations necessary to answer the primary and secondary aims. Obtain other studies as indicated for good clinical care.

History and Physical Examination: This should include signs and symptoms caused by the tumor/cancer, and determination of performance status or Lanski score. Patients must have a baseline neurological exam and neurological exam at the start of each new cycle. Weight, height and VS must be recorded.

Laboratory Evaluation:

-Hematology: Complete blood count, differential and platelet count every 2 weeks during the first cycle. If the patient does not experience any >Grade 1 hematologic toxicity during the first cycle, a CBC can be performed every 4 weeks on subsequent cycles, and as clinically indicated. If a patient experiences >Grade 1 hematologic toxicity (except for lymphopenia), they will continue to have weekly lab work until they have a cycle with no >Grade 1 toxicity. Following that cycle the lab work will be performed every 4 weeks (+/- 5 days) and as clinically indicated until completion of therapy. If the patient remains on-study beyond this and is hematologically stable, the patient will require lab work prior to every cycle as long as there is no >Grade 1 hematologic toxicity.

-Chemistries: CMP, magnesium, phosphorous, calcium and uric acid every other week during the first cycle. If the patient does not experience any >Grade 1 laboratory toxicity on the first cycle which is possibly, probably, or definitely related to Pegylated interferon, these can be performed every month on subsequent cycles, and as clinically indicated. If a patient experiences >Grade 1 laboratory toxicity they will continue to have weekly lab work until they have a cycle with no >Grade 1 toxicity. Following that cycle the lab work will be performed every 4 weeks and as clinically indicated until end of therapy.

If the patient remains on-study beyond this, the patient will require lab work prior to every cycle as long as there are no >Grade 1 laboratory toxicities.

-Calcium, phosphorous, magnesium and uric acid will be performed prior to each cycle and as clinically indicated.

-PT and PTT will be obtained at a baseline. Obtain later on only if clinically indicated.

-Endocrine Function Tests: First morning cortisol, free T4, TSH every six months or sooner if clinically indicated. Growth hormone testing to be done if clinically indicated.

-Urinalysis or urine dipstick is acceptable. Urinalysis will be obtained if urine dipstick is abnormal. If urine evaluation is normal, then check at the same time points as the brain MRI.

-Urine Pregnancy Test or Serum Pregnancy Test: required for females of childbearing potential. Additional pregnancy test per institutional guidelines. At Aflac, monthly pregnancy test for females of childbearing potential.

Radiology:

MRI of the brain/and or spine will be performed every 3 cycles throughout the duration of the treatment. Initial evaluation will be performed at the end of the cycle #3. Patients with a history of spinal disease will undergo a spine MRI at the same time points until there is no evidence of disease on 2 consecutive spine MRI's. All brain MRIs will include, if possible, diffusion-weighted, dynamic-enhanced, dynamic susceptibility, DT-MRI, and other MR sequences in addition to the standard MR sequences. All MRI's will be reviewed and interpreted with the neuroradiologist.

Quality Of Life Questionnaire:

- We have chosen the Peds-**FACT-Br**: Pediatric - For patients with Brain cancer, ages 7 to 12 year old or greater than 12 years. Additionally, we will include the parent QOL questionnaire. There are 2 versions, for patients younger than 12 years and for patients 12 years or older. To be administered prior to start therapy and q3 months at the same interval as MRIs. See appendix 2A, 2B, 2C and 2D.
- QOL questionnaires are not available for non -English speaking patients and they have not been validated in other languages. QOL questionnaires are not required for non-english speaking patients

Post-Therapy Evaluation

The following tests and procedures should be performed, if possible, at the time a patient comes off therapy, regardless of the reason for coming off therapy, unless the test or procedure has been performed in the past 14 days.

- History and physical examination.
- Performance status.
- Assessment of clinical toxicity/adverse events.
- Laboratory Assessment:
 - Complete blood count, differential and platelet count
 - SGPT (ALT), bilirubin (total and direct), BUN, creatinine, electrolytes, calcium,
 - Magnesium, phosphorus, uric acid.
 - Urinalysis
- MRI of Brain and/or spine.
- QOL questionnaire
- Ophthalmology evaluation

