Low grade gliomas are the most common pediatric central nervous system malignancies and can occur in different parts of the brain. Patients who undergo gross total resection, usually those with hemispheric tumors, have an excellent prognosis with surgical resection alone. Patients for whom gross total resection is not achievable have a significant risk of disease progression. Therefore, these patients benefit from adjuvant therapy. Multiple chemotherapy regimens have shown some efficacy in residual tumor, but more than 50% of patients experience recurrences. Radiation has been shown to be an effective therapy in the treatment of these tumors. Because of concerns regarding radiation toxicity especially in young children, and progression despite chemotherapy, novel approaches are needed. This protocol represents an attempt to measure the efficacy and safety of use of pegylated interferon for patients with recurrent, refractory Juvenile Pilocytic Astrocytomas (JPA) or optic pathway gliomas. It provides a different approach to the commonly used treatment modalities. Patients with progressive, refractory or symptomatic JPA who have received radiation and who have received at least one prior course of chemotherapy will be eligible for this study. All patients on the study will receive a course of pegylated interferon 1 mcg/kg/dose weekly lasting for up to 2 years. Response will be evaluated with MRI every 12 weeks. The objectives of this study are to determine the response of children with chemotherapy-refractory progressive JPA or optic pathway gliomas (OPG) to weekly pegylated interferon alpha-2b. The secondary objectives include to better identify the toxicities of weekly pegylated interferon alpha-2b in pediatric patients with unresectable, refractory, recurrent JPAs or optic pathway gliomas, to evaluate various magnetic resonance imaging techniques for noninvasive monitoring of metabolic and biologic changes in the tumors and to evaluate the quality of life for patients with recurrent, refractory JPAs who receive therapy with pegylated interferon alpha-2b. The primary end point is to determine the response rate. The secondary end point is to determine the Event Free survival. A two-stage design has been selected to evaluate the response rate. If the treatment demonstrates at least a 25% response rate, we would consider it a promising regimen for further study. A response rate less than 5% is considered evidence of unpromising regimen. Seventeen evaluable pediatric patients with JPA or OPG will be accrued. If at least 3 responders are seen among the 17 patients, this will be considered evidence of a promising response rate for further evaluation.

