Finally, 14 pediatric patients with multiply recurrent low-grade gliomas were treated with bevacizumab and irinotecan for at least twelve months of follow-up after completion of initial therapy. Median treatment duration was 12 months (range, 1 - 24 months). 12/14 patients had an objective response; two had stable disease, and no progressions. 13/14 patients progressed after stopping bevacizumab at a median of four months. Four patients were retreated with bevacizumab alone and all responded or stabilized on treatment. Bevacizumab-based therapy is successful at inducing LGG regression and stabilization after initial therapy or with repeated treatment, although nearly all patients' tumors will progress off-therapy. Toxicities are not insignificant but usually reversible (6). A subsequent report, gave additional details of responses after progression of LGG when retreated with bevacizumab in 4/4 patients, however alternative dose strategies such as bevacizumab as a single agent and interval does every 3 weeks were evaluated. [8]

Therashima et al evaluated pediatric patients with centrally located LGG who received either chemo or radiation to better understanding the risk factors along with the effects of interventions on long-term outcome through a retrospective chart review. Forty-seven patients with a median follow-up of 79 months were included in the analysis. The 5-year EFS and OS were 53% and 96%. The 5-year PFS for those that received radiation upfront was 76% vs. those who received chemotherapy as a first line 37%. $p=0.02$. The 5-year PFS after salvage RT was 55% for those who progressed after chemotherapy. [9]

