4.1 Overview of the treatment plan

Treatment with pegylated interferon alpha-2b must begin within 14 days of patient enrollment. Patients may be pre-medicated as needed with acetaminophen 10-15 mg/kg (maximum 650 mg per dose) or ibuprofen 10 mg/kg within 1 hour of receiving Pegylated interferon. The patients can continue on either acetaminophen or ibuprofen for up to 48 hours after Pegylated interferon injection. The maximum dose of ibuprofen in a 24-hour period will be 40 mg/kg. Ibuprofen for Adolescents and Adults the maximum daily dose: 2.4 grams in 24 hours. Premedication is optional.

Each cycle of therapy will consist of pegylated interferon alfa-2b administered subcutaneously once weekly (**+/- 5days**) for 4 weeks for up to 2 years. Each dose should be administered on the same day

each week. There will be no breaks between cycles. Total number of cycles 26. Each dose is 1µg/kg subcutaneously. Nursing staff will instruct the patients or their caregivers regarding sites of injection and injection technique. Teaching needs to be documented. Rotating the sites of injection is strongly recommended.

Patients and/or their caregivers will be asked to maintain a diary (Appendix 5) documenting the dose of pegylated interferon alpha-2b given, site of administration and any side effects. This diary will be reviewed at each clinic visit. Patients will return to the Aflac clinic prior to start next cycles.

Doses could be rounded up to the nearest upper 5mcg for easier administration. For patients whose weight is greater than 150kg the maximum dose of Pegylated interferon to be administered is 150mcg/dose/ week.

MRI brain and /or spine will be performed as a baseline within **30 days** of enrollment and subsequently every 3 cycles.

See section 7.1 for required observations prior to start therapy.

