4.3 Pegylated interferon Administration

Pegylated interferon will be administered weekly (**+/- 5 days**) at a dose of 1mcg/kg/dose via subcutaneous injection, approximately at the same time every week.

It is important to rotate the injection sites. Teaching will be done to the parents/guardian/patient in the first and/or second injection so the family will learn the technique and can continue to do it at home. Family/guardian will be provided with diaries to document compliance and side effects.

Patients may be pre-medicated with acetaminophen or ibuprofen. Specifically, patients can receive acetaminophen 10-15 mg/kg (maximum 650 mg per dose, maximum dose 4 grams/24 hours) or ibuprofen 10 mg/kg within 1 hour prior to receiving PEPegylated interferon. The patients can continue on either acetaminophen or ibuprofen for up to 48 hours after the pegylated interferon injection as needed. The maximum dose of ibuprofen in a 24-hour period will be 40 mg/kg or patients with weight for more than 45 kg is 2.4 grams/24 hours. Premedication is optional.

Pegylated interferon will begin a Cycle on Day 1 if **ANC \geq 1,000/ μ L, platelet count \geq 100,000/ μ L** (transfusion independent).

Dose calculations should be based on actual weight and adjusted as necessary prior to each cycle.

The maximum dose is 150 mcg.

Note: The calculated dose should be rounded to the nearest highest 5mcg of the prescribed dose for convenience of administration. Each cycle is 28 days. The total duration of the trial is 2 years a total of 26 cycles.

See Section 5.0 for Dose Modifications Based on Toxicities.

The therapy delivery maps (TDMs) for this cycle are on the next pages

Following completion of the first cycle, the Pegylated interferon cycle is repeated weekly for up to a total of 26 cycles, as tolerated and in the absence of disease progression (see Section 10.4 for Response Evaluation). If disease progression occurs, the patient will be taken off protocol therapy.

Subsequent Pegylated interferon cycles should begin on Day 29 or when ANC \geq 1,000/ μ L, platelet count \geq 100,000/ μ L (transfusion independent), whichever occurs later.

Therapy Delivery Plan

Pegylated interferon Dose 1mcg/kg/dose 4 consecutive weeks (28 days) will constitute one cycle. This therapy delivery map relates to all cycles of Pegylated interferon
	
Patient Name: _____ DOB _____

--	---

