7.2 Follow-up

- See COG Late Effects Guidelines for recommended post treatment follow-up:
<http://www.survivorshipguidelines.org/>

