8.2 Off Study Criteria

- Death.
- Lost to follow-up.
- Patient enrollment onto another treatment study with tumor therapeutic intent.
- Withdrawal of consent for any further data submission.
- The fifth anniversary of the date the patient was enrolled on this study.

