9.3.1.2 Secondary End Points

- Time to treatment failure (Event free Survival EFS) the time from study enrollment to tumor progression, tumor recurrence, death from any cause or occurrence of a second malignant neoplasm.
- Time to death (Overall survival OS) the time from study enrollment to death from any cause.

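### The plan gives two MRI rules that diverge once a cycle is delayed and schedules no tumour imaging after the removal scan, although EFS is an endpoint, follow-up runs to five years and no censoring rule is stated

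*Combined protocol and SAP*

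**What the plan says.** On-treatment imaging has two rules.

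- **Calendar rule.** The abstract says "Response will be evaluated with MRI every 12 weeks", and the schema repeats the 12-week interval.
- **Cycle rule.** Section 4.1 sets a baseline MRI within 30 days "of enrollment and subsequently every 3 cycles". The Radiology text of section 7.1 says "MRI of the brain/and or spine will be performed every 3 cycles throughout the duration of the treatment". The section 7.1 table places scans before cycles 4, 7, 10 and so on to 25, and the delivery map in section 4.3 places them after every third cycle and when clinically indicated.

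Cycle starts can move. Section 4.3 says "Subsequent Pegylated interferon cycles should begin on Day 29 or when ANC" and platelets recover, taking the later of the two. Section 5.2 makes a haematologic delay of 14 days or more a reason for dose reduction but states no maximum delay.

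When a patient comes off therapy for any reason, section 7.1 asks for one MRI, where feasible and unless done in the past 14 days. For the time after that, section 7.2 says only "See COG Late Effects Guidelines for recommended post treatment follow-up". Under sections 8.1 and 8.2 the patient stays in follow-up, with data required, until an off-study criterion is met; the last of these is "The fifth anniversary of the date the patient was enrolled on this study".

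Section 9.3.1.2 defines EFS as "the time from study enrollment to tumor progression, tumor recurrence, death from any cause or occurrence of a second malignant neoplasm", and objective 1.2.1 bases it on tumour measurements. Section 9.4 names Kaplan-Meier and log-rank methods and gives no censoring or missed-scan rule for EFS.

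**The concern.** Radiographic progression is dated by the scan that shows it. If scans move with cycle starts, a patient whose counts recover slowly is assessed later than one whose cycles run on time, and the EFS time carries a toxicity component.

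The period after therapy raises the same problem on a larger scale. It affects patients who leave without progression: for toxicity, by refusal, by physician decision, or after 26 cycles. They remain at risk for EFS for years with no planned assessment. Without a censoring rule, an analyst could carry them as event-free to last contact, which treats absence of a scan as absence of progression.

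At stake are the EFS estimate and, in part, the comparison of EFS across MR sequences in objective 1.2.3 and section 9.10, which needs scans to define events.

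**Working it through.** **1. The plan's own figures.** Cycle length and number come from section 4.3.

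- 3 × 28 = 84 days = 12.0 weeks, which matches the abstract when no cycle is late.
- 26 × 28 = 728 days = 104 weeks = 1.99 years, which matches the stated two years.
- Undelayed scans before cycles 4, 7, …, 25 fall at weeks 12, 24, 36, 48, 60, 72, 84 and 96.

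**2. Effect of delay on the cycle rule.** Interval = 84 days + the delays within the three cycles. The delays below are assumptions, because the documents give no delay rate.

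- One delay of 14 days: 84 + 14 = 98 days = 14.0 weeks.
- Three delays of 7 days: 84 + 21 = 105 days = 15.0 weeks.
- Three delays of 13 days, each short of the 14-day reduction trigger: 84 + 39 = 123 days = 17.6 weeks.

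**3. Time without a scheduled scan after therapy.** Five years = 5 × 365.25 / 7 = 260.9 weeks.

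- Completion of 26 undelayed cycles: 260.9 − 104 = 156.9 weeks, or 60% of follow-up.
- Stopping at week 12: 260.9 − 12 = 248.9 weeks, about 4.8 years.

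These figures take first dose as the day of enrolment. The 14 days allowed between the two shorten each gap by at most 2 weeks. They also assume that no other off-study criterion comes first.

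**4. What unscanned time could do to EFS (illustration only).** Assume exponential EFS with median m months, complete detection to month 24 and none afterwards, with patients carried as event-free. True five-year EFS is 0.5^(60/m); the curve would read 0.5^(24/m). The share of five-year events falling after month 24 is (0.5^(24/m) − 0.5^(60/m)) / (1 − 0.5^(60/m)).

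| Assumed median (months) | Share of events after month 24 | True 5-year EFS | EFS as read |
|---|---|---|---|
| 12 | 23% | 3% | 25% |
| 24 | 39% | 18% | 50% |
| 36 | 46% | 31% | 63% |
| 48 | 49% | 42% | 71% |

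For patients who stay on therapy for the full two years this overstates the bias, since clinical progression and routine scans would reveal some later events. If patients are instead censored at the last MRI, this bias is removed, but EFS much beyond two years cannot be estimated.

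**5. Primary design.** The section 9.2 design (0 of 9, then 2 of 17 as rejection limits) reproduces exactly: type I error 0.0466, power 0.812, early-termination probability 0.630, expected size 11.96. Enrolment is 17 / 0.85 = 20. None of these uses EFS.

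**The case against.** The strongest reply is that the plan already has a calendar intention and several other routes to detecting progression. The abstract and schema say 12 weeks, and section 7.1 ties the quality-of-life forms to the MRIs at three-month intervals. Section 10.4 counts clinical progression as well as radiographic. A neurological examination precedes each cycle, the delivery map allows scans when indicated, and section 4.2.4 requires an MRI within 5 days when steroids are increased for worsening symptoms. EFS is also a secondary estimate in a single arm of 17. All of this stands and limits the size of the problem. It does not reconcile the two rules or supply a censoring rule.

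It can also be said that a scan at the end of cycle 3 need not wait for cycle 4 to start. That protects the first interval from one delay, but the delay then falls into the next interval.

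Four stronger readings are tempting, and the documents do not support them.

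- *Imaging ignores the calendar and simply ends with therapy.* The 12-week wording and the removal scan contradict this.
- *Intervals of 18 weeks from three 14-day delays would be common.* Under sections 5.0 and 5.2, two such haematologic delays use both permitted reductions and a third ends therapy. For non-haematologic toxicity, section 5.1 ends treatment if recovery takes more than 14 days. Half the scan interval is therefore not a fair general measure of detection lag.
- *At least three of the five years lack scheduled scans.* The 728 days hold only without delay, and completion is defined as 26 cycles, so treatment might run longer.
- *Events will concentrate off therapy.* Section 2.2 reports that "13/14 patients progressed after stopping bevacizumab at a median of four months", but that is another drug. Section 2.6 describes a patient in a peginterferon series, in another tumour type, with a complete response lasting more than 10 years. Neither shows where events will fall here.

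**Conclusion.** The point holds in two parts of unequal weight. During treatment, two scan rules diverge once a cycle is delayed, so the timing of EFS assessment depends partly on toxicity. The slip is a matter of weeks, and its frequency cannot be derived from the documents.

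After treatment the gap is much larger: about 157 of 261 weeks for a patient who completes 26 undelayed cycles, and about 249 for one who stops at week 12. The direction of bias is upward if unscanned time counts as event-free. Its size rests on the EFS distribution, on how often clinics scan in routine care, and on the censoring actually applied, none of which the documents give. The external guideline cited in section 7.2 is not part of the documents, so what imaging it may recommend was not assessed.

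A reader might infer that scheduled imaging supports EFS to 24 months for everyone. It does not: for a patient who stops early, scheduled imaging ends at the removal scan. This is worth correcting because it is cheap, but it does not threaten the response decision.

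**What to change.** 1. Reconcile sections 4.1 and 7.1 and the delivery map with the abstract and schema: MRI every 12 weeks from first dose, within the stated window, whatever the cycle number or delay. The window itself needs one value, since section 4.0 allows 5 days and section 7.0 allows 96 hours.
2. For patients off therapy without progression, record the date and result of each routine surveillance MRI. State in section 9.4 that EFS is censored at the last tumour assessment and not at last contact. Report the number censored early with reasons, because censoring related to toxicity may be informative.
3. Present EFS beyond the period of scheduled imaging as descriptive only, and say that for patients who stop early this period ends at the removal scan. Routine scans will still be irregular, so item 2 limits the dependence on local practice without removing it.

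The cost is protocol wording, some data collection from routine care, an occasional extra scan in patients with delayed cycles, and a shorter interpretable EFS horizon. The sample size does not change.
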